13. PRIOR AND CONCOMITANT MEDICATIONS

Prior and concomitant medications, as collected on the *Concomitant Medication* eCRF page, will be summarized for the SAF, by age category and overall. They will be presented by PT and coded using the latest version of the World Health Organization Drug Dictionary (WHO-DD).

See [Appendix 1](#) for handling of partial dates for medications. In the case where it is not possible to define a medication as prior, concomitant, or post treatment, the medication will be classified by the worst case (i.e. concomitant).

- ‘Prior’ medications are medications which started and stopped prior to the first dose of study medication.
- ‘Concomitant’ medications are medications which:
 - started prior to, on or after the first dose of study medication and started no later than 6 days following end of study medication,
 - AND ended on or after the date of first dose of study medication or were ongoing at the end of the study.
- ‘Post’ medications are medications which started more than 6 days following the last dose of study medication.

Prior and concomitant medications observed during the Follow-up period will also be summarized by CBD status.

Prior and concomitant medications will also be listed.

In addition, AED medication(s), including stopping or starting medication(s), may be adjusted throughout the trial to maximize seizure control based on tolerability as judged by the investigator. AEDs are recorded on the *Concomitant Medication* eCRF page where the “Reason for medication” is ticked “Antiepileptic drug (AED)”.

Changes in AED medication(s) will be analyzed as follows:

- The number of different AEDs a subject took during the study will be summarized
- A bar chart will present the mean number of seizures versus the number of unique AEDs taken during the study for each age category and overall and by type of seizures (separate graphs for tonic and atonic seizures).
- AEDs will be flagged in the listing for all prior and concomitant medications

As for overall concomitant medications, incidence of AEDs will be summarized for each PTs by age category and overall.

AEDs observed during the Follow-up period will also be summarized by CBD status.

Document: C:\Users\q832483\Documents\Insys CSR\Pending\Ready for QC\New folder\Statistical Analysis Plan.docx
Author: [REDACTED] Version Number: V1.0 Final
Version Date: 04APR2017

Template No: CS_TP_BS016 – Revision 3
Effective Date: 01May2012

Reference: CS_WI_BS005

14. STUDY MEDICATION EXPOSURE

Exposure to study medication in days will be presented for the SAF, by age category and overall. The following parameters will be summarized:

- Modal dose (defined as the dose with the longest exposure),
- Total duration of study medication at any dose
- Total duration of each dose
- Number of subjects dosed per time points

The date of first study medication administration will be taken from the *Study Drug Administration* eCRF page. The date of last study medication will be taken from the *End of Treatment* eCRF page. In the case of missing data on these eCRF pages, the *Subject Diary – Study Medication Record* eCRF page will be used in order to determine the first and last date of study medication.

Interruptions, compliance, and dose changes are not taken into account for duration of exposure.

The corresponding listing will present first/last dose dates, does the subject complete the treatment duration, reason for end of treatment and duration of exposure (days).

In addition, dose modifications will be summarized by age category and overall in terms of:

- Number of subjects with at least one dose modification (as defined [Section 14.1](#))
- Number of subjects with at least one dose changed
- Number of subjects with at least one dose interrupted
- Number of subjects with dose permanently discontinued
- Number of subjects per reason of dose modification
 - Adverse event
 - Lack of efficacy
 - PK-analysis result
 - Other

If a subject experiences several dose modifications for the same reason, he will be counted only once for this reason. However, in the case a subject experiences several dose modifications due to different reasons, he will be counted once for each reason.

A supportive listing will display all the relevant administration details including data/time/interval of each administration, volume planned/administered, reason if dose not administered and amount of water consumed after dosing.

Exposure data coming from the *Subject Diary – Study Medication Record* eCRF page will also be listed.

Document: C:\Users\q832483\Documents\Insy CSR\Pending\Ready for QC\New folder\Statistical Analysis Plan.docx
Author: [REDACTED] Version Number: V1.0 Final
Version Date: 04APR2017

Template No: CS_TP_BS016 – Revision 3
Effective Date: 01May2012

Reference: CS_WI_BS005

14.1. DERIVATIONS

The following derivation will be used to calculate the duration of exposure:

- Duration of exposure (days) = date of last study medication administration – date of first study medication administration + 1.

A dose modification is defined as any change in dose, dose interruption or dose permanently discontinued.

15. STUDY MEDICATION COMPLIANCE

The starting dose of the study medication will be determined by the study previously completed by the subject. Dosing of the study medication may be increased or decreased at any dose based on efficacy and tolerability up to a maximum of 40 mg/kg/day.

Noncompliance is defined as taking <80% or >120% of the study medication during any evaluation period (i.e., visit to visit).

Compliance to study medication will be presented for the SAF.

15.1. DERIVATIONS

Compliance to study medication will be based on the volume of medication and calculated as follows:

- "Per Visit" Compliance to study medication will be calculated as follows:

$$\frac{\text{Sum of administered volumes during the week before Visit X}}{\text{Sum of planned volumes during the week before Visit X}} \times 100$$

The compliance per visit will be summarized and reasons for which dose not administered will be listed. The compliance will be clustered as follows: <50%, [50%; 80%, [80%; 100%, [100%; 120%, >120%.

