Physical examination and neurological examination ^k	X	X				X		X	X
Dispense (D), review (R), and collect (C) subject seizure and dosing diary ^l					D	D/R/C		R/C	
Dispense (D) and collect (C) study drug and review (R) dosing procedures		D/R	D/R/C	D/R/C	D/R/C	D/R/C		C	
Administer morning dose of study drug in the clinic		X				X			
AEs and SAEs	X	X	X	X	X	X		X	X
Blood draw for plasma levels		X			X	X		X	X

Assessments ^a	Visit 1 (14 Day Screening Period ^b)	Treatment Period						Final Visit / Discontinuation Visit ^d (Visit 10) Week 48 ±10 days ^e (if not conducted at a normally scheduled visit)	Follow-up Visit Two weeks after Final Visit / Discontinuation Visit (Visit 11) ±5 days
		Visit 2 (Day 1 ^c)	Visit 3 (Week 1) ±3 days	Visit 4 (Week 2) ±3 days	Visits 5, 6, & 7 Monthly: (Weeks 4, 8 & 12) ±7 days	Visits 8, 9, Quarterly: (Weeks 24 and 36) ±10 days ^d			
Investigator and Parent(s)/caregiver(s) CGI-S ^m	X	X			X	X		X	X
Investigator and Parent(s)/caregiver(s) CGI-I ^m					X	X		X	X
IPES ^{n, o}		X			X	X		X	X
VABS ^{n, p}		X						X	
C-SSRS ^q	X	X			X	X		X	X
Reminders for next visit ^s	X	X	X	X	X	X			

^a At Visits 2, 5, 6, 7, 8, 9 and 10 all assessments are to precede administration of the morning dose of the investigational product (i.e., the subject should arrive for their study visit without having taken the morning dose of the investigational product). See Section 5.1 for more details.

^b A Screening Period (Visit 1) will be required only for all subjects that do not rollover within 14 days of completing their previous study.

^c Visit 2 (Day 1) may occur simultaneously with Day 11 from INS011-014-029 or within 14 days of Visit 1 (Screening Visit) for INS011-14-030. All assessments (except vital signs) completed within 14 days prior to administration of the first dose of Cannabidiol Oral Solution in INS011-14-030 may be used for Visit 2 (Day 1) (to avoid repetition of procedures).

^d Subjects will receive two daily oral doses of Cannabidiol Oral Solution for approximately 48 weeks or until the investigational product is successfully approved for marketing in the US (whichever occurs earlier), inclusive of their treatment on the previous

study, unless they are discontinued due to a reason described in Section 3.4.3. After 12 weeks, study visits will be completed at a quarterly frequency; the definition of quarterly is every 12 weeks (e.g., Weeks 24 and 36).

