4.10 Treatment Compliance

The subject seizure and dosing diary will include a record of the date and time of each administration of the investigational product. Diary data will be collected for one week (7 days) prior to each quarterly visits.

Subjects exhibiting poor compliance should be counseled on the importance of good compliance to the study dosing regimen. Noncompliance is defined as taking <80% or >120% of the investigational product during any evaluation period (i.e., visit to visit).

Any departures from the intended regimen must be recorded in the eCRF.

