4.11 Study Medication Accountability

The Investigator, a member of the investigational staff, or a hospital pharmacist must maintain an adequate record of the receipt, distribution, and collection (of unused supplies)

of all investigational product using the Drug Accountability Form. These forms must be available for inspection at any time.

All supplies of the investigational product should be accounted for at the termination of the study and a written explanation provided for discrepancies. All unused supplies and packaging materials are to be inventoried and returned to the Sponsor or a designee by the Investigator. The Investigator is not permitted to return or destroy unused clinical drug supplies or packaging materials unless authorized by the Sponsor or designee.

If the study is terminated, discontinued, suspended, or completed, all unused supplies of the investigational product may be destroyed via the use of a third-party vendor or be returned to the Sponsor or a designee after the final drug accountability check has been performed. A certificate of destruction will be provided to the Sponsor.

All regulations issued by the DEA in regards to the accountability of Schedule I medications will be followed (e.g., prevention of diversion).

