6.3.2 Additional Information to be Recorded in Subject Seizure and Dosing Diary

The subject seizure and dosing diary will include a record of the date and time of each administration of the investigational product in the one week prior to Visits 8, 9, and 10.

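### Compliance is calculated from one week before a visit, but noncompliance is defined over the whole interval between visits, so the reported figure can misclassify subjects in either direction.

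*SAP*

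**What the plan says.** The definition is the same in both documents. Protocol 4.10: "Noncompliance is defined as taking <80% or >120% of the investigational product during any evaluation period (i.e., visit to visit"). SAP 15: "Noncompliance is defined as taking <80% or >120% of the study medication during any evaluation period (i.e., visit to visit").

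SAP 15.1 then gives a single formula for per-visit compliance, expressed as a percentage. Numerator: "Sum of administered volumes during the week before Visit X". Denominator: "Sum of planned volumes during the week before Visit X". Results are grouped into classes with cut points at 50%, 80%, 100% and 120%, so the class limits include the two noncompliance thresholds.

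On the data available, Protocol 4.10 says: "Diary data will be collected for one week (7 days) prior to each quarterly visits". Protocol 6.3.2 says the diary records the "date and time of each administration of the investigational product in the one week prior to Visits 8, 9, and 10". Protocol 6.3.1 has the first diary handed out at Visit 7 (Week 12).

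Study drug is handled at every treatment visit. The Table 1 row "Dispense (D) and collect (C) study drug and review (R) dosing procedures" shows dispensing and collection at Visits 3 to 9 and collection at Visit 10. Under Protocol 4.11, site staff "must maintain an adequate record of the receipt, distribution, and collection (of unused supplies").

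SAP 3.3, which lists changes from the protocol, mentions only the replacement of dose-level summaries by age-category summaries.

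**The concern.** The rule and the formula refer to different periods. A table headed as per-visit compliance and cut at 80% and 120% will be read as applying the visit-to-visit rule, yet no step extends one week to the interval. A programmer who follows the SAP exactly will place some subjects on the wrong side of the SAP's own threshold.

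What is at stake is the reading of long-term exposure. Long-term safety is the primary objective. SAP 14 computes duration of exposure from first and last dose dates and states that interruptions, compliance and dose changes are left out of it. The compliance table is therefore the main summary of how much of the planned drug was taken.

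**Working it through.** Neither document states a compliance figure, so there is nothing to reproduce. The check sets the period the formula uses against the period the definition names.

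**Inputs**
- Quarterly interval: 12 weeks = 84 days (Protocol Table 1, footnote d).
- Diary: 7 days before Visits 8, 9 and 10 (Protocol 4.10 and 6.3.2); none before Visit 7 at Week 12 (Protocol 6.3.1).
- Full schedule: 48 weeks = 336 days.
- Dosing: twice daily, so 14 doses in a diary week and 168 in 84 days.
- SAP 15.1 does not name the diary. The link rests on the diary being the only at-home dosing record the protocol specifies.

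**Coverage**
- Each quarterly interval: 7/84 = 8.3%. If the ±10-day windows make the interval 64 or 104 days, 7/64 = 10.9% and 7/104 = 6.7%.
- Intervals ending at Visits 3 to 7: 7 + 7 + 14 + 28 + 28 = 84 days, with 0 diary days.
- Full 48-week schedule: 3 × 7 / 336 = 21/336 = 6.25%. Up to 20 of a maximum 80 subjects come from INS011-15-054 and may have fewer intervals here; 7/84 per quarterly interval is unchanged.

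**How far the two measures can differ**

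Let c be compliance in the diary week and q compliance in the other 77 days. Then interval compliance = (7c + 77q)/84. The values of c and q below are assumptions; the documents give no adherence data.

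| c (reported) | q | Interval compliance | By definition | Reported class |
|---|---|---|---|---|
| 100% | 60% | (7 + 46.2)/84 = 63.3% | noncompliant | at least 80% |
| 100% | 75% | (7 + 57.75)/84 = 77.1% | noncompliant | at least 80% |
| 11/14 = 78.6% | 100% | (5.5 + 77)/84 = 98.2% | compliant | below 80% |
| 0% | 100% | 77/84 = 91.7% | compliant | below 50% |

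With c = 100%, the interval falls below 80% whenever q < (0.8 × 84 − 7)/77 = 60.2/77 = 78.2%.

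**Steady adherence**

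Assume equal dose volumes and independent doses, each taken with probability p. Reaching 80% needs at least 12 of 14 doses in the diary week, or at least 135 of 168 in the interval.

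| p | P(diary week ≥ 80%) | P(interval ≥ 80%) |
|---|---|---|
| 0.75 | 0.28 | 0.06 |
| 0.85 | 0.65 | 0.96 |
| 0.90 | 0.84 | 1.00 |

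So even without any change of behaviour near visits, the one-week figure passes too many subjects at p = 0.75 and flags too many at p = 0.85.

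**Source of the volumes**

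The formula needs volumes. Protocol 6.3.2 describes the diary as holding dates and times. SAP 14 mentions a supportive listing with planned and administered volume, so volumes may be captured on an eCRF page, but SAP 15.1 does not say which page feeds the formula.

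**The case against.** The strongest reply is that SAP 15.1 is open about its one-week window, that the window follows from how the diary is designed, and that little depends on it. There is no hypothesis test and no per-protocol set. Adverse event incidences are not adjusted for compliance. Noncompliance is also captured elsewhere: SAP 9 summarises investigational-product compliance deviations, SAP 14 summarises dose changes and interruptions, and Protocol 4.10 requires departures from the regimen to be entered in the eCRF. All of this stands and limits the consequence. It does not remove the contradiction between SAP 15 and SAP 15.1.

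Three stronger readings are tempting, and the documents do not support them.
- *Compliance will be overstated.* Protocol 4.6 recommends a call to prompt families to start recording that week, and one might infer that it is the best-supervised week. That is inference: no adherence data are given, and the working shows errors both ways.
- *No compliance can be computed for Visits 3 to 7.* The diary cannot supply it, but the listing in SAP 14 suggests a second source of administered volumes. Its coverage cannot be judged from the documents; it may hold only in-clinic doses.
- *Trough levels become hard to interpret.* Protocol 1.1.4.1 gives a half-life range of 18 to 33 hours (intravenous or inhaled). Seven days is 168 hours, or 168/33 = 5.1 half-lives at the long end. On that range the week before the visit is the relevant window for a trough at Visits 8 to 10, and Protocol 6.2 records the time of the last dose.

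The feasibility of a volume-based measure is also fairly questioned. Protocol 4.11 requires accountability records, but neither document says that returned volume is measured or held in the database.

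**Conclusion.** The point holds as an inconsistency between definition and derivation. The per-visit figure rests on 8.3% of each quarterly interval and, on the diary alone, on none of the first 12 weeks. It does not measure visit-to-visit compliance and can misclassify subjects in either direction; the net direction is unknown. SAP 3.3 does not disclose the departure.

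The coverage figures assume nominal visit timing and that the diary supplies the formula. The 6.25% also assumes a full 48-week schedule in this study. The effect is limited to a descriptive summary used to read long-term exposure. The plan should be corrected, but no other planned analysis depends on it.

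**What to change.** In SAP 15.1, define compliance for each visit interval from Visit 2 to Visit 10 as

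(volume dispensed − volume returned) / (planned volume for that interval, from the recorded doses and dose changes) × 100.

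Classify this with the 80% and 120% limits, and keep the diary-week value as supportive. This would cover all 84 days of each quarterly interval and the five intervals of the first 12 weeks.

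**Cost.** It goes beyond SAP wording. Someone must confirm that returned volumes are recorded and can be brought into the analysis database. The denominator must follow dose changes, and any recalculation of dose volume by weight, within each interval. Spilled or unreturned bottles add noise, and returned volume shows what left the bottle, not what was swallowed.

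**If the volumes are not available,** relabel the figure as diary-week compliance (Visits 8, 9 and 10), name the eCRF page it comes from, state that it does not assess the visit-to-visit definition, do not classify subjects as noncompliant from it, and record the departure in SAP 3.3. That costs only wording.

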16. PHARMACOKINETIC AND EFFICACY OUTCOMES

16.1. PHARMACOKINETIC

PK analyses will be described in a separate SAP.

16.2. EFFICACY OUTCOMES

Efficacy related data do not represent endpoints for this long-term safety study but they will be recorded and

Document: C:\Users\q832483\Documents\Insy CSR\Pending\Ready for QC\New folder\Statistical Analysis Plan.docx
Author: [REDACTED] Version Number: V1.0 Final
Version Date: 04APR2017

Template No: CS_TP_BS016 – Revision 3
Effective Date: 01May2012

Reference: CS_WI_BS005

[REDACTED]
analyzed in terms of:

- Control of seizures (frequency, duration, and severity of seizures compared to each baseline as defined [Section 6.2](#))
- Qualitative subject status (CGI-S, CGI-I, IPES)

The analysis of efficacy-related data will be performed for the SAF.

No statistical inferential procedures will be performed.

16.2.1. SEIZURES-RELATED DATA

In this study, seizure frequency, duration, and severity will be assessed to monitor seizure control achieved by long-term treatment with Cannabidiol Oral Solution. Seizures will be observed and recorded using a patient reported outcome (PRO) instrument (i.e., subject/caregiver diaries). Seizures are collected at week 24, week 36 and final visit and they will be compared to the baseline from the previous study.

16.2.1.1. Seizures-Related Variable(s) & Derivation(s)

The following variables will be used to assess the control of seizures:

- Type of seizures:
 - Tonic: body stiffening, upward deviation of the eyes, pupil dilation, and altered respiratory patterns
 - Atonic: brief loss of muscle tone and consciousness, that may result in an abrupt fall
 - Myoclonic: sudden muscle jerks and including infantile spasms
 - Tonic-clonic: jerking preceded by stiffening
 - Clonic: repeated jerking
 - Absence: lapses of awareness, sometimes with staring
 - Febrile: seizure of various types (especially tonic-clonic) associated with high fever
 - Focal: typically involving 1 side and/or region of the body, twitching, and grimacing
 - Atypical absence: staring (as in an absence seizure), but subject may also be somewhat responsive.
- Seizure frequency:

For tonic and atonic seizures, the number of seizures will be recorded. For other types of seizures, the frequency will be reported by range as follows:

- None
- 1 to 5 seizures
- 6 to 19 seizures
- 20 to 50 seizures

Document: C:\Users\q832483\Documents\Insys CSR\Pending\Ready for QC\New folder\Statistical Analysis Plan.docx
Author: [REDACTED] Version Number: V1.0 Final
Version Date: 04APR2017

Template No: CS_TP_BS016 – Revision 3
Effective Date: 01May2012

Reference: CS_WI_BS005

[REDACTED]

- > 50 seizures.
- Seizure severity:

The assessment of seizure severity will be recorded by the parent(s)/caregiver(s) in the subject seizure and dosing diary. Seizure severity will be categorized as:

- Mild
- Moderate
- Severe

Overall seizure severity will be captured using the CGI-S as described in [Section 16.2.2](#).

- Seizure duration:

The approximate timing of seizure will be recorded by the parent(s)/caregiver(s) in the subject seizure and dosing diary.

16.2.1.2. Missing Data Methods for Seizures-Related Variable(s)

All data will be evaluated as observed; no imputation method for missing values will be used.

The eCRF includes the following question on each study day: "Did the subject experience any seizures?". If the response to this question is no, it will be assumed that the subject does not have any seizures on that day. If the question is not answered, it will be not assumed that the subject does not have any seizures that day (i.e., it will be assumed that the question is inadvertently not answered).

16.2.1.3. Analysis of Seizures-Related Variable(s)

Seizure-related parameters will be summarized as follows:

- Number of subjects (and corresponding percentage) that experienced, by maximum severity, a tonic and atonic seizure, per time point and age category.
- Descriptive statistics (n, mean, SD, median, minimum, and maximum) of the actual number and duration of tonic and atonic seizures, by time point and age category.
- Descriptive statistics (n, mean, SD, median, minimum, and maximum) of the change from baseline in the number and duration of tonic and atonic seizures, by time point and age category.
- Number of subjects by maximum severity, maximum number of seizures and seizure duration for each other types of seizures by time point and age category.
- For each tonic and atonic seizure type, figures will display:
 - Number of seizures per subjects over time by age category
 - Average number of seizures over time by age category and by modal dose category, where modal doses will be clustered as follows:]0;10],]10;20],]20;30],]30;40].

Supportive listings will also be performed for tonic and atonic seizures, and for other types of seizures separately. The listings will include all the related data recorded in the *Subject Diary – Seizure Record* eCRF page.

Document: C:\Users\q832483\Documents\Insy CSR\Pending\Ready for QC\New folder\Statistical Analysis Plan.docx
Author: [REDACTED] Version Number: V1.0 Final
Version Date: 04APR2017

Template No: CS_TP_BS016 – Revision 3
Effective Date: 01May2012

Reference: CS_WI_BS005

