6.3 Efficacy

6.3.1 Seizure Control

In this study, seizure frequency, duration, and severity will be assessed to monitor seizure control achieved by long-term treatment with Cannabidiol Oral Solution. Seizures will be observed and recorded using a patient reported outcome (PRO) instrument (i.e.,

subject/caregiver diaries). The exact format and version(s) of diary to be used will also be included in the eCRF. Diaries will be dispensed at Visits 7, 8, and 9 (Weeks 12, 24, and 36) and reviewed and completed pages collected (if applicable) during each visit.

For the purposes of this study, only observable seizures will be quantified in the one week prior to Visits 8, 9, and 10. All seizures should be recorded by the parent(s)/caregiver(s) and/or subject (if applicable) in the diary.

Given that continuous seizures may be observed in some subjects (i.e., multiple seizures may occur without break), it may not be possible to accurately record all seizures for these subjects. If necessary, the parent(s)/caregiver(s) or subject (if applicable) will, at a minimum, categorize the seizure frequency (for seizures others than tonic or atonic seizures) by range (i.e., diaries will record the count of seizures per day as >50 seizures/day, 20 to 50 seizures/day, 6 to 19 seizures/day, 1 to 5 seizures/day, or no seizures).

The subject and/or his/her parent(s)/caregiver(s) are responsible for completing the diary. The party who is primarily responsible will be chosen by the Investigator in consultation with the subject's parent(s)/caregiver(s). If a pediatric subject will be entering diary data, the parent(s)/caregiver(s) should provide guidance and monitor accuracy and completeness.

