8.3.6.1 Seizure-related Data

All seizure-related parameters (in terms of raw data and percentage change from baseline) will be listed and summarized by dose and for all subjects using descriptive statistics (mean, number, SD, median, minimum, and maximum values for continuous variables).

No statistical inferential procedures will be performed.

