6.6. COMMON CALCULATIONS

For quantitative measurements, change from baseline will be calculated as:

- Test Value at Visit X – Baseline Value

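### Tonic and atonic seizure counts have no stated unit and are not divided by answered diary days, so unanswered or out-of-window days can look like a change in seizure control

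*SAP*

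**What the plan says.** **Variable.** SAP 16.2.1.1: "For tonic and atonic seizures, the number of seizures will be recorded". The other seven seizure types are reported by range.

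**Summaries.** SAP 16.2.1.3 gives descriptive statistics "of the actual number and duration of tonic and atonic seizures, by time point and age category", and also "of the change from baseline in the number and duration of tonic and atonic seizures, by time point and age category". SAP 6.6 defines change as "Test Value at Visit X – Baseline Value". Protocol 8.3.6.1 is no more specific about the unit: "All seizure-related parameters (in terms of raw data and percentage change from baseline) will be listed and summarized by dose". The number of seizures also feeds the figures in SAP 16.2.1.3 and the chart of mean seizures against number of antiepileptic drugs in SAP 13.

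**Unanswered days.** SAP 16.2.1.2: "All data will be evaluated as observed; no imputation method for missing values will be used". It adds: "If the question is not answered, it will be not assumed that the subject does not have any seizures that day".

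**Diary period and time points.** Protocol 6.3.1: "only observable seizures will be quantified in the one week prior to Visits 8, 9, and 10". SAP 6.4 then assigns each dated seizure record to a time point by study day. Week 24 is Days 158-178 and Week 36 is Days 242-262.

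**Comparator.** SAP 16.2.1 compares on-study seizures with the previous-study baseline. SAP 6.2 quotes a baseline definition from INS011-14-029 only (the last non-missing measurement before first dose). Neither document gives the number of baseline diary days in INS011-14-029 or INS011-15-054.

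**The concern.** A seizure count means something only in relation to the time over which seizures were observed. The plan recognises that an unanswered day is missing rather than seizure-free, but carries this into no derivation. If the number at a time point is the sum over the diary week, an unanswered day contributes exactly what a seizure-free day contributes. The difference from baseline then mixes seizure control with diary completion.

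At stake is the objective of continued efficacy in maintaining seizure control. There is no control arm and no test, so a reader will judge tonic and atonic seizures from these descriptive changes and the figures built on the same counts.

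**Working it through.** The documents state no power, rate or standard deviation that bears on this point, so there is no figure of the plan's own to reproduce. The check takes the number as the period total and holds the true seizure rate constant. The apparent change is then

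(answered on-study days / answered baseline days) - 1.

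**1. Unanswered on-study days.** The planned diary is 7 days (Protocol 6.3.1). A baseline of 7 answered days is assumed.
- 1 unanswered: 6/7 - 1 = -14.3%
- 2 unanswered: 5/7 - 1 = -28.6%
- 3 unanswered: 4/7 - 1 = -42.9%

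A true 30% rise with 2 unanswered days gives 1.3 x 5/7 - 1 = -7.1%, so a worsening appears as a small improvement.

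On the SAP's absolute scale, assume 5 seizures a day and 80% of on-study days answered. The expected change is 5 x 7 x 0.8 - 5 x 7 = 28 - 35 = -7 seizures with no true change. A simulation of 80 subjects on these assumptions gave a mean of -7.0 for the raw count and 0.0 for the rate per 7 answered days. The 5 per day and the 80% are illustrations; the documents give neither.

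**2. Unanswered baseline days.** With 7 answered on-study days and 5 answered baseline days, 7/5 - 1 = +40%. The sign reverses.

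**3. Baseline length.** This is unknown from these documents, so the range is shown as an assumption, with 7 answered on-study days:
- 3 days: 7/3 - 1 = +133%
- 7 days: 0%
- 14 days: 7/14 - 1 = -50%
- 28 days: 7/28 - 1 = -75%

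**4. Table A and complete diaries.** The Week 24 window is the target day plus or minus 10 (168 - 10 = 158; 168 + 10 = 178), the same tolerance as the visit itself (Protocol 5.2.5). The diary, however, lies before the visit. For a visit on Day V the diary days are V - 7 to V - 1, and the number inside the window is min(7, V - 158).
- V = 158: 0 days
- V = 161: 3 days (3/7 - 1 = -57.1%)
- V = 164: 6 days (-14.3%)
- V = 165 to 178: all 7 days

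The days cut off fall between the Week 12 window (ends Day 91) and the Week 24 window, so Table A assigns them to no time point. At V = 158 no diary day is left, and the SAP does not say whether the result is zero or missing. The same holds for Week 36 visits on Days 242-248, where min(7, V - 242) gives 0 to 6.

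**5. With a rate.** Using seizures on answered days / answered days x 7 at both ends, the expected change is 0 when the true rate is unchanged and recording is unrelated to that day's seizures, whatever the number of answered days.

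**The case against.** The strongest reply is that the SAP never says the number is a weekly sum. The diary question is asked daily, Protocol 6.3.1 states its ranges per day, and other seizure types are summarised by a maximum. If the number were a daily value averaged over answered days, unanswered days would cause no such bias and SAP 16.2.1.2 would work as written. SAP 8 also refers to output templates that are not among these documents and might settle the unit. This stands as far as it goes: what is certain is an undefined derivation, and the bias depends on the period-total reading. A per-day average would still have to be stated, and the wording used points to a plain count.

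A reader might infer that the baseline diaries differ in length from the on-study week. The documents do not show this; two complete 7-day baselines would remove that part altogether. Nor do they show that incomplete diaries always favour the drug, since step 2 runs the other way and no completion rates are given.

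On duration, a subject with no seizures in the week has no value, so seizure-free subjects may leave that summary. That is not an error in itself. Duration given a seizure is a legitimate quantity, and total seizure time with zeros measures something else, closer to burden. What is missing is a statement of which is meant.

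It is also fair that efficacy data are descriptive and expressly not endpoints, that global impression scales and seizure severity inform the same objective, and that the diary records will be listed.

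**Conclusion.** The point holds in a limited form. No section of the protocol or SAP gives the tonic and atonic count a unit, a day-based denominator or a minimum number of answered days. On the plain period-total reading, and with a complete 7-day baseline, the artefact is -14% to -43% for 1 to 3 unanswered on-study days. The Table A cut-off does not depend on poor completion: it affects any Week 24 visit on Days 158-164 if the windows are applied as written.

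The count problem covers tonic and atonic seizures only; ranges and maxima for the other types respond differently to missed days. Bias from baseline length remains an open question. The matter should be fixed, but it does not touch the safety evaluation, which is the study's primary purpose.

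**What to change.** For tonic and atonic seizures, the SAP should:

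- Define seizure rate = seizures on answered diary days / answered diary days x 7, at each visit and at baseline where the feeder study holds answered-day data. Use it in the actual, change and figure outputs.
- Assign the 7 pre-visit diary days to their visit instead of using the Table A window.
- Report answered days per time point and apply a prespecified minimum, for example 4 of 7, after that assignment. Applied to the Table A windows, a 4-of-7 rule would discard complete diaries for Week 24 visits on Days 158-161, which keep only 0 to 3 days.
- State the baseline diary period for each feeder study, and say where a baseline rate cannot be formed.
- State that the duration summary is conditional on having a seizure, and show the number of seizure-free subjects beside it. Total seizure time per 7 answered days may be added as a separate quantity.

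**Cost.** This needs an SAP amendment, a derived variable and a changed assignment rule. The daily yes/no question is already on this study's eCRF (SAP 16.2.1.2), and Protocol 8.2.1 allows changes of method before database lock without a protocol amendment. Subjects with very sparse diaries lose a time point. Whether answered-day data can be retrieved from INS011-14-029 and INS011-15-054 is not shown here and must be checked.
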